### 4.4.2 Formulation, Packaging, and Labeling (Product name and Trademark)

The seasonal TIV produced by GPO uses embryonated chicken eggs. This is a split virion, inactivated vaccine. The vaccine source strains are:

- X-275 reassortant of A/Michigan/45/2015 (H1N1)pdm-09
- X-263B reassortant of A/Hong Kong/4801/2014 (H3N2)
- BX-35 reassortant of B/Brisbane/60/2008

Each dose of Tri Fluvac contains a total of 45 micrograms ( $\mu$ g) hemagglutinin (HA) per 0.5 ml dose (15  $\mu$ g HA per strain per dose). Tri Fluvac is manufactured and formulated as a multiple-dose vial vaccine (2 doses) using thimerosal at relatively low concentration as preservative ( $\leq 7.5 \ \mu$ g mercury/ dose). Each 0.5 ml dose of vaccine may contain residual amounts of ovalbumin ( $\leq 5.0 \ \mu$ g), formaldehyde ( $\leq 50 \ \mu$ g), tween 80 ( $\leq 250 \ \mu$ g), triton x-100 ( $\leq 5 \ \mu$ g) and gentamicin (not more than 0.05  $\mu$ g).

The vaccine should be administered as a single 0.5ml intramuscular injection, preferably in the region of the deltoid muscle of the non-dominant arm. The vaccine should not be injected in the gluteal region or areas where there may be a major nerve trunk. It should not be injected intravascularly. A needle of  $\geq 1$  inch is preferred to ensure sufficient penetration of the muscle tissue in some adults. It is recommended that small syringes (0.5ml or 1ml) should be used to minimize any product loss.

The vaccine should be stored at 2-8°C (in a refrigerator), not frozen and protected from TighCS COMMITTEE

FACULTY OF TROPICAL MEDICINE

ไตยาลัยม

Allow vaccine to reach room temperature and shake before use. Between uses, return the multidose vial to the recommended storage conditions between 2-8 °C and use within 24 hours. Do not freeze. Discard if the vaccine has been frozen.

# 4.5 Comparator

The comparator will be provided in prefilled, single dose, disposable syringes.

Brand Name	A commercially available, licensed vaccine
Common or Non-Proprietary Name of Drug Substance	Influenza vaccine (split virion, inactivated)
Dosage Form(S) and Strength(s)	
 
Suspension, Each 0.5-ml dose contains 15 µg of haemagglutinin (HA) of each of the following three influenza virus strains recommended for southern hemisphere 2017
 
An A/Michigan/45/2015 (H1N1) pdm09-like virus
 
An A/Hong Kong/4801/2014 (H3N2)-like virus
 
A B/Brisbane/60/2008 –like virus
 

Route(s) of Administration	Intramuscular injection
Country from which the clinical supplies were obtained for the Lot to be Used in this Clinical Trial	Thailand
Market status in the above mentioned country	Market Approval

# 4.6 Dosage, Preparation, and Administration of Study Products

# 4.6.1 Dosage and Schedule

A single dose level of the GPO Tri Fluvac will be evaluated in this study. The dose will be a total of 0.5 mL containing at least 15 mcg HA for each component. The vaccine is to be delivered intramuscularly preferably into the deltoid of the non-dominant arm.

# 4.6.2 Precautions and Warnings

- The GPO Tri Fluvac is only to be used for healthy adults 18 to 49 years of age participating in this study who meet the inclusion/exclusion criteria. It is forbidden to use the vaccine for any other purpose.
- Strict compliance with Thai regulations on the use of vaccines and biologicals is required.
- Vaccination should be intramuscularly into the deltoid of the participant's non-dominant arm. The dominant arm may be used if the participant prefers it or if the non-dominant arm would make it difficult to interpret the reactogenicity (for example, stated or scar).
- Study product syringes that have had temperature excursions may not be used. Contact GPO for further instructions.
- Only health workers who have been trained for this research and minister study were study administer study were study administer study were study at the study of the study

product to enrolled participants, assuring proper intramuscular injection technique and sterile injection.

- Only one person may be injected with one needle and syringe.
- Study participants must remain in the clinic and be monitored for 30 minutes after vaccination.
- The study vaccination clinic should have adequate facilities for monitoring and treating any reactions. Drugs to treat anaphylaxis must be available, as must specialist doctors for such an emergency. Prompt referral to additional needed facilities must be available.

# 4.6.3 Preparation and Administration

An unblinded staff will prepare and administer vaccine to each participant. None of the unblinded staff will be involved in any reactogenecity and other safety evaluations.

To prepare and administer study product, vaccination facilities and investigators must comply with any applicable regulations. The step-by-step instructions for the investigator (or delegated staff) are as follows:

- Wash hands or use gel disinfectant. Prepare the study vaccine/placebo, needles, syringes, and sharps safety box ahead of time.
- Specific study procedures will be developed and include selecting the appropriate study product. Careful records must be maintained to ensure and document that each participant receives the correct product.
- Make sure sufficient equipment is available to provide every participant with a safe injection and to dispose of injection materials safely.
- Make sure emergency drug and equipment kits are available in both the vaccination area and the observation area.
- Greet the participant in a friendly manner. Ask whether he/she has any questions or concerns about injection and respond to his/her questions and concerns in a truthful and pleasant manner.
- Confirm the participant identity.
- Ensure the participant is seated or lying down.
- Inform the participant that everyone will be preferably vaccinated in the deltoid of their non-dominant arm.
- Put on gloves.
- Instruct the participant to put the hand on the hip and show them the deltoid.
- Disinfect the skin at the injection site.
- Inject intramuscularly the entire contents of the syringe into the deltoid region of the participant's non-dominant arm.
- While the plunger is still depressed, remove the needle from the participant's arm.
- Apply cotton swab with pressure to the injection site.
- Dispose of needle and syringe as one unit in a sharps container that is only used for this MMITTEE study.
   Faculty of tropical medicine
   MAHIDOL UNIVERSITY

APPROVED

- Record the date of vaccination and vaccine vial number on the participant's vaccination record.
- Ask the participant to rest for 30 minutes.
- Blinded staff will provide the diary card, ruler, thermometer and explain how to use them for recording symptoms. Remind them of upcoming phone calls/visits.
- For 30 minutes following vaccination, observe the participant and ask about the participant's well-being.
- Before the participant leaves, review with them when to seek medical assistance if adverse events occur that require medical evaluation and treatment.

# 4.7 Modification of Study Product for a Participant

There is no dose adjustment for the product in the study.

# 4.8 Accountability Procedures for Study Product

The study vaccine and comparator will be kept in a secure place in cold storage at the study clinic segregated from other products, under a lock (the refrigerator or the room where product is stored) and with controlled access. During the study, the investigator or the person in charge of research product management will record information related to the delivery of study product to the trial site, conduct inventory at the trial site, check the number of doses given to the participants, check the number of unused doses, and return both, the used and the unused vials to GPO after completing the study, if directed. Standard procedures will be followed at the trial site to maintain proper transport, receipt, storage, and return of study products.

In the case of interruption of the cold chain, the Principal Investigator or qualified designated staff member must contact GPO to get further instructions. The investigator must receive the written consent from GPO before clinical trial products can be used.

# 4.9 Assessment of Compliance with Use of the Study Products

Compliance with use of the study products will be closely monitored during the trial by the research team, GPO and trial monitors.

# 4.10 Concomitant Medications/Treatment

Concomitant medications for the treatment of pre-existing medical condition, and per AEs / SAEs reporting period outlined in Table 2 will be documented throughout the course of the study.

Treatment of conditions that are not exclusionary should continue, if needed by the participant. Subsequent changes in concomitant treatment during the trial must also be reflected in the CRF.

Women included in the trial who are using hormonal contraception for pregnancy prevention should continue using these products through Day 60. Use of such products will be recorded in the CRF.

# 4.11 Unauthorized Products

The following products are not authorized to be used during the study:

- Any concomitant medicine or biologic specifically prescribed for the treatment of a condition which is an exclusion criterion for participation in the trial.
- All non-study vaccines or biologics (including blood product) before Day 21ETHICS COMMITTEE

Other concomitant products are allowed

พยาลัยม

FACULTY OF TROPICAL MEDICINE

MAHIDOL UNIVERSITY

Participants will be educated not to take analgesic or antipyretic drugs in a preventive way as such medications might change the reactogenicity profiles of the study vaccine and comparator. However, the participants may take antipyretic drugs after injection, in order to treat any related symptoms.

# 5. Study Enrollment and Withdrawal

## 5.1 Study Participants, Source of Participants

This trial will enroll 945 male and female adults age 18 to 49 years. Participants will be recruited by referral, by word-of-mouth or other study materials, which will be approved by the ethical committee. The study staff will follow inclusion/exclusion criteria to determine eligibility. Screening evaluation will be conducted on all individuals interested in joining the study who have signed the study consent form. Results of the screening evaluation will be reviewed with each participant, regardless of eligibility.

# 5.2 Participant Inclusion/ Exclusion Criteria

(1) Inclusion Criteria

All participants must meet all of the following criteria to be considered eligible to participate in the study:

- Age 18-49 years old on the day of screening, having Thai ID card or equivalent
- Able to read and write in Thai and sign written informed consent form
- Able to attend all scheduled visits and to comply with all trial procedures.
- Healthy or medically stable, as established by medical history and physical examination. For individuals with medical conditions, symptoms/signs, if present must be stable under control or unchanged for the past three months. If medication is used to treat the condition, the medication dose must have been stable for at least one month preceding vaccination.

For female participants:

- Not breast feeding, non-pregnant (based on negative urine pregnancy test) and no plan to become pregnant up to Day 60.
- Women who are not surgically sterile (hysterectomy or tubal ligation) or post-menopausal for more than one year must be willing to use effective contraceptive method to prevent pregnancy until Day 60 after vaccination. Effective methods include intrauterine device, hormonal contraceptives (oral, injectable, patch, implant, ring) or double barrier contraceptives (condom or diaphragm with spermicide). Women with credible history of abstinence may be enrolled at the discretion of the investigator.
- (2) Exclusion Criteria

Participants meeting any of the following criteria will be excluded from participation:

- Participation in another clinical trial involving any therapy within the previous three months or planned enrollment in such a trial during the period of this study.
- Hypersensitivity after previous administration of any vaccine.
- Having a history of H1N1, H3N2 or FluB infection within 3 months preceding enrollment to the trial
- Vaccination against influenza in the past 6 months preceding enrolment to the trial
- Receipt of any non-study vaccine within four weeks prior to enrollment or refusar over postpone receipt of such vaccines until after the Day 21 visit.
- History of bronchial asthma, chronic lung diseases, chronic rhinitis
- History of immunodeficiency state

วิตยาลัยม
- History of immunosuppression < 6 months prior to immunization
- History of anaphylactic or other allergic reactions to influenza vaccine or any vaccine component or excipient (e.g. gentamicin or thimerosal)
- History of Guillain-Barré Syndrome.
- Having acute infection with fever > 38 degree Celsius and noninfectious diseases (within 72 hours) preceding enrollment in the trial
- The volunteers who have been taking immunoglobulin products or have had a blood transfusion during past 3 months before the beginning of the trial or planned receipt of such products prior to the Day 21 visit.
- Current alcohol abuse or drug addiction that might interfere with the ability to comply with trial procedures
- Any condition that in the opinion of the investigator would pose a health risk to the subject if enrolled, or could interfere with the evaluation of the Vaccine

# **5.3 Treatment Assignment Procedures**

# 5.3.1 Randomization Procedures

This is a double-blind, randomized, and controlled trial with two groups: vaccine and comparator. Each participant will be assigned a unique screening number assigned by the investigator after signing the informed consent. After an individual is determined to be eligible for study participation, the participant will be randomized by assigning a unique participant identification number from the randomization schedule.

The complete randomization schedule that contains the participant identification number and the corresponding randomization assignment will be produced using computer software prior to the initiation of the study. The permuted randomized block design procedure will be used to generate the randomization schedules using varying block sizes. Treatment assignments will be completely randomized within each block, and the blocks will be ordered (permuted) randomly to ensure treatment balance during enrollment and maintenance of the blind.

The Investigator will maintain a screening/enrollment log. The log will contain essential information including participant ID number, date of screening, gender, date of birth, whether or not the participant meets eligibility criteria, whether the participant is enrolled and date, and if not enrolled, reason why the participant was not enrolled or not randomized.

Once a participant identification number has been assigned, it will not be used again. Additional participants may be randomized into the study in the case of any participant who is randomized but does not receive any study vaccine. Study participants will be randomly assigned to one of the two treatment groups. Blinding through randomization number will be maintained for the investigator who assesses immunogenicity and safety.

An un-equal randomization of 2:1 (Group V : Group C) lists will be generated by an independent statistician at the Center of Excellence for Biomedical and Public Health Informatics (BIOPHICS) at the Faculty of Tropical Medicine. The computerized randomization will be generated as a block of 3. The sample size of 945 (630 Group V: 315 Group C), the randomization numbers will be generated for 166 blocks. However, with the consideration of any unusual events that might unexpectedly happen during the trial, an extra 4 blocks will be generated as a backup set for VED replacement. This extra list will be kept separately and will be used only when necessary. The randomization will be kept in secured safe-box at BIOPHICS and will be opened only when necessary. The MAHIDOL UNIVERSITY

randomization blocks of treatment materials will be sent only to the study coordination center for study vaccine preparation and distribution to study sites. All other study investigators as well as the volunteers will be blinded from the randomized codes. The codes will be open at the study conclusion or upon special request due to unexpected adverse event occurs. The emergency unblinding process will be done only when there is a special request for ethical and emergency clinical concerns by the sponsor or ethical committee or the principal investigator.

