- Day 60 (+14 days): Phone visit for reports of adverse events and ILL if any

ETHICS COMMITTEE FACULTY OF TROPICAL MEDICINE MAHIDOL UNIVERSITY

ตยาลัยม

• Day 90 (+7 days): Blood specimen collection for immune response, follow-up and reports of any AEs/SAEs.

Blood specimens will be collected on Day 0 prior to vaccination, Day 21 and Day 90 following immunization. Serum samples will be separated from whole blood samples for HI assays. Subjects will be asked to report any adverse events and influenza-like illness (ILI) that occur after immunization. Concomitant medication will be collected. At Day 60, there will be a reminder call for reporting any adverse events and ILI. In addition, a throat or nasopharyngeal swab for influenza virus will be performed in those reported ILI. The study schedule and activities are summarized below in Table 2.

Safety will be assessed in all participants through Day 90. The justification for the three month follow-up, rather than six month follow-up is that: 1) in general, the safety of inactivated influenza vaccines is well-established, 2) the phase 1/2 trial showed very limited reactogenicity and no association with unsolicited adverse events.

Immunogenicity will be assessed by HI in a representative subset of at least 586 participants who received vaccine and 293 who receive comparator. In order to select the participants to test in an unbiased way, baseline and post-vaccination blood will be obtained from all the participants. An unblinded statistician will prepare a list of samples to be tested based on a random selection of participants, however neither the laboratory nor the clinical investigators will know the treatment received for each participants.

The study will test a seasonal TIV composed of the following strains:

- A/Michigan/45/2015 (H1N1)pdm-09-like virus
- A/Hong Kong/4801/2014 (H3N2)-like virus
- B/Brisbane/60/2008-like virus

ETHICS COMMITTEE FACULTY OF TROPICAL MEDICINE MAHIDOL UNIVERSITY

APPROVE

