# 5.3.2 Blinding and Unblinding Procedures

The randomization will be conducted by an organization or individual not involved in day to day the conduct of the study. The investigator will assign the unblinded staff responsible for vaccine preparation, administration, handling and accountability and to ensure that blinding is protected throughout the study procedures and no other site personnel involved in the conduct of the study has access to the information. After assessment of eligibility of a new subject, the Subject Number will be assigned to each subject sequentially in the order they are enrolled. The unblinded staff will prepare and administer vaccine/comparator according to randomization list provided by BIOPHICS. The unblinded staff will be responsible to keep the randomization list in a safe, locked and secured place with no access by other site personnel until the database is locked.

The randomization lists will be provided to GPO for them to label the study vaccine and comparator syringes and then placed in a sealed envelope immediately afterward. It will be opened only after the clinical trial database is declared complete and locked. In the case of any unblinding, researchers must report this in writing to the overseeing ethics committee.

The vial labeling will be done at GPO before study vaccine and comparator are shipped. Study product injected into each participant will be recorded on the Case Report Form (CRF) using the exact allocation code for each product received by each participant.

The allocation codes link treatment identification with each participant identification number. These will be maintained in a secure location, by an individual not involved in the conduct of the study. If the investigator determines that it is necessary to unblind a participant, for example because a participant experiences an SAE possibly related to receipt of study treatment, then the treatment allocation to the participant will be communicated to the investigator.

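### Protocol 5.3.1 contradicts itself: 166 blocks of 3 supply 498 allocations, not 945, and a fixed block of 3 conflicts with the varying block sizes stated in the same section

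*Protocol*

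**What the plan says.** Section 5.3.1 of the protocol describes the randomisation twice. The general description calls for a permuted block procedure to "generate the randomization schedules using varying block sizes". The specific description, later in the section, sets a 2:1 ratio and says "The computerized randomization will be generated as a block of 3". For the sample of 945 (630:315) it then says "the randomization numbers will be generated for 166 blocks". It adds that "an extra 4 blocks will be generated as a backup set for" replacement, kept separately from the main list.

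Three statements elsewhere bear on the consequences:

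- Section 5.3.2 says "the Subject Number will be assigned to each subject sequentially in the order they are enrolled".
- The same section provides that, if the investigator finds it necessary to unblind a participant (a possibly related SAE is the example given), "then the treatment allocation to the participant will be communicated to the investigator".
- Section 4.1 says of the HI testing that "neither the laboratory nor the clinical investigators will know the treatment received".

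The SAP contains no block size and no block count.

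**The concern.** The number of blocks, the block size and the sample size are tied together in one short stretch of text, and they do not agree. Followed literally, the list would run out a little past half of enrolment. The general and specific descriptions also give incompatible block structures, so anyone checking that the randomisation was followed (a monitoring task under section 13.3) has no single specification to check against.

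A second issue depends on which statement governs. If blocks really are of size 3, that size is printed in a document the blinded investigators hold, and subject numbers run in enrolment order. Block boundaries could then be worked out, and unblinding one participant would carry information about the other two in that block. Investigators judge the severity and relatedness of unsolicited adverse events, so their blinding matters for a primary safety endpoint.

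**Working it through.** **Inputs**

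- Total 945, split 630:315, ratio 2:1, block size 3, 166 blocks, 4 backup blocks: Protocol 5.3.1.
- H3 sample size 293 + 586 = 879, with 7% not in the ATP cohort: Protocol 11.2.
- Actual enrolment 945: registration record at the front of the SAP.

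**1. Is 945 itself sound?** The H3 seroconversion calculation (0.535 in both arms, margin 0.10, one-sided 0.025, power 80%, ratio 2:1) reproduces 293 and 586. Then 879 / 0.93 = 945.2, stated as 945. The target reproduces and is used consistently elsewhere in the protocol (section 1, 4.1, 5.1), so the fault lies in the randomisation text.

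**2. What does the text supply?** Allocations = blocks × block size.

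| Blocks of 3 | Allocations | Vaccine : comparator | Short of 945 |
|---|---|---|---|
| 166 (as stated) | 498 | 332 : 166 | 447 (47.3%) |
| 170 (with backup) | 510 | 340 : 170 | 435 (46.0%) |
| 315 (= 945 / 3) | 945 | 630 : 315 | 0 |
| 319 (= 315 + 4 backup) | 957 | 638 : 319 | none |

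The total of 498 matches none of the totals in the sample-size tables.

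**3. Could another block size explain 166?** An average of 945 / 166 = 5.69 would be needed. A 2:1 ratio requires multiples of 3:

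- size 6: 166 × 6 = 996 (51 more than 945)
- size 9: 166 × 9 = 1,494
- size 12: 166 × 12 = 1,992

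No single size gives exactly 945. A mix can. With x blocks of 3 and 166 − x of 6, 3x + 6(166 − x) = 945 gives x = 17, so 17 blocks of 3 and 149 of 6 (51 + 894 = 945). No such mix is stated, and it would contradict the block of 3. Either the count or the size may be the wrong entry, and the documents do not show which.

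**4. What would one unblinding reveal?** This assumes that the list is used in order and that the block boundaries are known. Before any unblinding, each participant has a 2/3 chance of vaccine and a 1/3 chance of comparator.

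| Block | Unblinded member | Left in block | Each other member is comparator |
|---|---|---|---|
| 3 (2 vaccine, 1 comparator) | comparator | 2 vaccine | 0: both are known to be vaccine |
| 3 | vaccine | 1 vaccine, 1 comparator | 1/2 = 50% |
| 6 (4 vaccine, 2 comparator) | comparator | 4 vaccine, 1 comparator | 1/5 = 20% |
| 6 | vaccine | 3 vaccine, 2 comparator | 2/5 = 40% |

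Only the block of 3 identifies anyone outright, and then only when the unblinded participant received the comparator.

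**The case against.** The strongest reply is that this is an editorial slip with no demonstrated effect. Enrolment reached 945, the ratio and target split are clear, and no margin, error rate, power figure or analysis set depends on the block count. That is right about the primary analysis, and it limits the weight of the point. It does not remove the contradiction: 945 enrolled suggests that a longer list existed, but says nothing about its block structure.

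It can also be said that a list only has to hold at least 945 entries, so 166 blocks of 6 (996) would be enough and the count may be correct. This is a fair reading, but it makes the stated block size wrong instead.

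The blinding argument is a chain of conditions. Block size 3 must govern, the list must be used in strict order, someone must be unblinded, that person must be a comparator recipient for anyone to be identified, and a blinded assessor must work out the boundary. The documents give no expected number of unblindings. Controls also exist: emergency unblinding is by special request (5.3.1), any unblinding is reported in writing to the ethics committee (5.3.2), and under the SAE procedure in Appendix B the Safety Medical Team decides whether to unblind serious unexpected reactions. Participants record solicited reactions themselves after the 30-minute check, and investigators need not assess their causality when onset falls in the solicitation period (8.2). The HI laboratory is blinded. All of this stands, and it confines the risk to judgements on a block's remaining members.

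**Conclusion.** The concern holds. Section 5.3.1 is wrong as written on two counts:

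- **Count.** The stated count and size yield 498 allocations (510 with the backup) against 945 required; at size 3 the count should be 315, not 166.
- **Block size.** Fixed blocks of 3 and varying block sizes cannot both describe the same list.

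These conclusions need only figures printed in the section and multiplication. Which entry is in error cannot be settled from the documents.

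The point should be corrected, but it does not threaten the non-inferiority comparison. There is no sign that the list ran out. The blinding consequence is secondary, rests on the assumptions in step 4 of the working, and reaches at most the two other members of a block for each unblinded participant.

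**What to change.** State one scheme in section 5.3.1.

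- **Preferred:** permuted blocks of varying sizes in multiples of 3, giving at least 945 allocations (630:315) plus the backup. Delete the fixed block of 3 and the count of 166. Keep the sizes out of the protocol, in a restricted randomisation document available for audit and withheld from blinded site and sponsor personnel. The unblinded staff necessarily hold the list, as do those who label at GPO ("The randomization lists will be provided to GPO for them to label the study vaccine").
- **Minimum:** keep block size 3, correct the count to 315 blocks plus the backup, and delete the reference to varying sizes. This cures the arithmetic and the contradiction but leaves a published fixed block of 3, so the within-block inference remains possible.

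If the list already exists, report the block sizes and the number of blocks actually used; the registration record gives the trial as completed, so this is the practical remedy.

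The cost is a few lines of wording. The list needs regenerating only if randomisation has not been completed and it holds fewer than 945 allocations. Varying sizes may leave an imbalance of a few participants if the last block is not filled.
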